4.4 Early study termination

The study can be terminated at any time for any reason by Novartis. Should this be necessary, the patient should be seen as soon as possible (for a prematurely withdrawn patient. The investigator may be informed of additional procedures to be followed in order to ensure that adequate consideration is given to the protection of the patient's interests. The investigator will be responsible for informing IRBs and/or ECs of the early termination of the trial.

5 Population

5.1 Patient population

The patient population will consist of male or female individuals, aged 18 years or older who have been diagnosed with Polycythemia Vera (PV, see [Appendix 1](#)), and who are hydroxyurea (HU) resistant or intolerant and have no other treatment options or are not eligible for a clinical study with an investigational medicinal product for PV.

Patients in the study may not participate in any other interventional clinical studies of other investigational agents or devices. Patients who have discontinued the study may not be re-enrolled for a second course of treatment.

The investigator or designee must ensure that only patients who meet all the following inclusion and none of the exclusion criteria are offered treatment in the study.

5.2 Inclusion criteria

Written informed consent must be obtained prior to any screening procedures.

Patients eligible for inclusion in this study have to meet **all** of the following criteria at screening:

1. Male or female aged 18 or over,
2. Confirmed diagnosis of PV according to the revised World Health Organization (WHO) criteria (see [Appendix 1](#)), with resistance or intolerance to hydroxyurea.
3. ECOG performance status of 0, 1, or 2 at Baseline,
4. Peripheral blood blast count of 0% at screening,
5. Must have recovered or stabilized sufficiently from adverse drug reactions associated with any prior treatments before beginning treatment with ruxolitinib,
6. Does not have access to a comparable or satisfactory alternative treatment (i.e., comparable or satisfactory treatment is not available or does not exist),
7. Is not eligible for participation in any of the ruxolitinib ongoing clinical trials or has recently completed a clinical trial that has been terminated and, after considering other options (e.g., trial extensions, amendments, etc.), the clinical team has determined that treatment is necessary and there are no other feasible alternatives for the patient),
8. Is not being transferred from an ongoing clinical trial for which he/she is still eligible.

5.3 Exclusion criteria

Patients eligible for this study should not meet **any** of the following criteria at screening:

Lab and Clinical Abnormalities

1. Subjects with known hypersensitivity to ruxolitinib or any of its excipients
2. Patients with severely impaired renal function defined by:
Serum creatinine > 2 mg/dL ($> 176.8\mu\text{mol/L}$)
3. Patients with inadequate liver function defined by any of these:
 - Total bilirubin $\geq 2.5 \times$ ULN and subsequent determination of direct bilirubin $\geq 2.5 \times$ ULN;
 - Alanine aminotransferase (ALT) $> 2.5 \times$ ULN; Aspartate aminotransferase (AST) $> 2.5 \times$ ULN.
4. Platelet counts $< 50 \times 10^9/\text{L}$ or an Absolute Neutrophil Count (ANC) $< 1 \times 10^9/\text{L}$ at screening.

Concurrent Diseases / Medication History

5. Patients being treated concurrently with a strong (potent) systemic inhibitor or inducer of CYP3A4 (refer to [Appendix 7](#)) at the time of Screening.
6. Presence of active bacterial, fungal, parasitic, or viral infection which requires therapy.

7. Known history of human immunodeficiency virus (HIV) infection or other immunodeficiency syndromes such as X-linked agammaglobulinemia and common variable immune deficiency
8. Acute viral hepatitis or active chronic hepatitis B or C infection.
9. History of progressive multifocal leuko-encephalopathy (PML).
10. Impairment of gastrointestinal (GI) function or GI disease that may significantly alter the absorption of ruxolitinib (e.g., ulcerative diseases, uncontrolled nausea, vomiting, diarrhea, malabsorption syndrome, small bowel resection).
11. History or current diagnosis of uncontrolled or significant cardiac disease, including any of the following:
 - Myocardial infarction within last 6 months
 - Uncontrolled congestive heart failure
 - Unstable angina within last 6 months
 - Clinically significant (symptomatic) cardiac arrhythmias (e.g., sustained ventricular tachycardia, and clinically significant second or third degree AV block without a pacemaker)
12. Significant concurrent, uncontrolled medical condition which, in the investigator's opinion, would jeopardize the safety of the patient or compliance with the protocol.
13. Subjects undergoing treatment with another investigational medication or having been treated with an investigational medication within 30 days or 5 half-lives (whichever is longer) prior to the first dose of study drug.
14. Patients with a history of malignancy in the past 3 years except for treated, early-stage squamous or basal cell carcinoma.
15. Receiving PEG-IFN-alpha-2a within 5 weeks of first dose.

Ability to comply with Protocol

16. Patients who are unable to comprehend or unwilling to sign an informed consent form (ICF).

Pregnancy and Birth Control

17. Pregnant or nursing (lactating) women
18. Women of child-bearing potential, defined as all women physiologically capable of becoming pregnant, unless they are using highly effective methods of contraception throughout the study duration inclusive of 30 day safety follow up. Highly effective contraception methods include:
 - Total abstinence (when this is in line with the preferred and usual lifestyle of the subject). Periodic abstinence (e.g., calendar, ovulation, symptothermal, post-ovulation methods) and withdrawal are not acceptable methods of contraception
 - Female sterilization (have had surgical bilateral oophorectomy with or without hysterectomy), total hysterectomy or tubal ligation at least six weeks before taking study treatment. In case of oophorectomy alone, only when the reproductive status of the woman has been confirmed by follow up hormone level assessment
 - Male sterilization (at least 6 months prior to screening). The vasectomized male partner should be the sole partner for that subject.

- Use of oral, injected or implanted hormonal methods of contraception or placement of an intrauterine device (IUD) or intrauterine system (IUS) or other forms of hormonal contraception that have comparable efficacy (failure rate <1%), for example hormone vaginal ring or transdermal hormone contraception (in case of oral contraception you should have been using the same pill on a stable dose for a minimum of 3 months before screening)

Women are considered post-menopausal and not of child bearing potential if they have had 12 months of natural (spontaneous) amenorrhea with an appropriate clinical profile (e.g. age appropriate, history of vasomotor symptoms) or have had surgical bilateral oophorectomy (with or without hysterectomy) or tubal ligation at least six weeks ago. In the case of oophorectomy alone, only when the reproductive status of the woman has been confirmed by follow up hormone level assessment is she considered not of child bearing potential.

6 Treatment

6.1 Study treatment

INC424/ruxolitinib tablets will be the only investigational drug in this study.

6.1.1 Dosing regimen

The starting dose of ruxolitinib will be 10 mg bid (see [Section 6.3.4](#) and [Section 6.3.7](#) for exceptions). A standardized dosing paradigm will be used to determine dose adjustments for safety and efficacy so that each patient is titrated to their most appropriate dose (see [Section 6.3.1](#) of the protocol). The ruxolitinib dose should not exceed 25 mg bid and should not be less than 5 mg once a day unless there is an adverse event that warrants interruption.

Patients may self-administer daily ruxolitinib tablets qd or bid (see [Section 6.3.4](#) and [Section 6.3.7](#) for exceptions) orally, without regard to food, in an outpatient setting in accordance with the specified dosing schedule provided by the investigator.

Patients who miss a dose should be counseled to take the next dose as scheduled and not to take double the dose.

Table 6-1 Dose and treatment schedule

| Study treatments | Pharmaceutical form and route of administration | Dose | Frequency and/or Regimen |
|--------------------|---|--|--|
| INC424/ruxolitinib | Tablet for oral use | Starting dose 10 mg bid (approximately 12 hours apart: morning and night), to be increased or decreased (5 mg steps) per standardized dosing paradigm and not to exceed 25 mg bid (see Section 6.1.1) | Daily, unless instructed to temporarily withhold dosing for safety |

The investigator will instruct the patient to take the study drug as per protocol. All dosages prescribed and dispensed to the patient and all dose changes during the study should be recorded on the Dosage Administration Record eCRF.

6.1.2 Ancillary treatments

All patients should receive low dose aspirin (75-150 mg/day), as standard of care for PV patients, unless medically contraindicated. In this case, other prophylactic antithrombotic agents may be used. Higher doses of aspirin (> 150 mg/day) should not be used except when medically indicated per the treating physician.

Aspirin and other antithrombotic use will be documented in the eCRF.

6.1.3 Rescue medication

Not applicable.

6.1.4 Guidelines for continuation of treatment

Not applicable.

6.1.5 Treatment duration

Patients may continue ruxolitinib treatment until they experience any of the following:

- Disease progression determined by the local investigator (see [Appendix 4](#) and [Appendix 5](#)),
- Unacceptable toxicity that precludes further treatment,
- Start of a new anti-cancer therapy,
- Pregnancy,
- Treatment is discontinued at the discretion of the investigator or patient,
- Lost to follow-up or withdrawn consent,
- Death,
- Study terminated by the sponsor,
- Study is completed (see definition below).

Treatment duration is considered “completed” three months after ruxolitinib becomes commercially available in the patients participating country or by 31 December 2017, whichever comes first, and the patient should be transitioned to commercial product. Study sites should stop all patients’ study participation on the ETP at this time.

6.2 Dose escalation guidelines

Not applicable to the study.

6.3 Dose modifications

6.3.1 Dose escalations due to inadequate efficacy

The initial dose of ruxolitinib will be 10 mg bid up to Week 4 (see [Section 6.3.4](#) and [Section 6.3.7](#) for exceptions). Based upon hematology and spleen palpation results, the dose of ruxolitinib **may** be increased by 5 mg bid from the previous 4 weeks in patients who meet the following conditions:

1. Inadequate efficacy as demonstrated by one or more of the following:

- a. Hct > 45%,
- b. WBC > upper limit of normal range,
- c. A clinically relevant increase in palpable spleen as determined by the investigator.

AND

2. The patient should have demonstrated adequate safety to increase the dose with all of the following:
 - a. Platelet count $\geq 140 \times 10^9/L$,
 - b. Hemoglobin $\geq 12 \text{ g/dL}$
 - c. ANC $\geq 1.5 \times 10^9/L$.
 - d. No treatment-related toxicity must have occurred with the current dose level, resulting in treatment reduction or interruption in the previous 28 days.

The total dose should never exceed 25 mg bid.

Table 6-2 Ruxolitinib allowed dose escalation due to inadequate efficacy

| Week of Study | Maximum Dose | Based on (no potent CYP3A4 inhibitor use) |
|---------------|--------------|---|
| 1 to 4 | 10 mg bid | Eligibility for study |
| 5 to 8 | 15 mg bid | Hematology, spleen palpation, AEs |
| 9 to 12 | 20 mg bid | Hematology, spleen palpation, AEs |
| 13 to EoT | 25 mg bid | Hematology, spleen palpation, AEs |

6.3.2 Dose reductions due to hematological changes

For patients who do not tolerate the protocol-specified dosing schedule, dose adjustments are permitted in order to allow the patient to continue the study treatment. Dose reductions or interruptions for hematological changes are described in [Table 6-3](#).

The objective of the ruxolitinib dose adjustment rules is to optimize response for each individual patient (namely achieve and maintain Hct < 45% and normalize WBC and PLT counts) while avoiding specific Grade 2 or higher cytopenias.

Doses may be titrated based on safety. Treatment should be interrupted for platelet counts less than $50 \times 10^9/L$ or absolute neutrophil counts less than $0.5 \times 10^9/L$.

The treatment should also be interrupted when hemoglobin is below 8 g/dL (80 g/L).

Dose reductions should be considered if the platelet counts decrease below $100 \times 10^9/L$ with the goal of avoiding dose interruptions for thrombocytopenia. The dose reduction should also be considered if hemoglobin decreases below 12 g/dL (120 g/L) and is recommended if hemoglobin decreases below 10 g/dL (100 g/L).

After dose interruption, when blood counts recover, dosing may be restarted at 5 mg twice daily and gradually increased based on careful monitoring of blood cell counts.

All dose changes should be recorded on the Dosage Administration Record eCRF.

The following guidelines should be applied:

[figure not shown]

Table 6-3 Dose modifications for hematologic toxicity

| Hematology Parameters | Reduction or Interruption |
|--|--------------------------------------|
| Platelet count < 100 x 10 ⁹ /L | Dose reduction should be considered. |
| Platelet count < 50 x 10 ⁹ /L | Treatment should be interrupted. |
| Absolute neutrophil count < 0.5 x 10 ⁹ /L | Treatment should be interrupted. |
| Hemoglobin < 12 g/dL (120 g/L) | Dose reduction should be considered |
| Hemoglobin < 10 g/dL (100 g/L) | Dose reduction is recommended |
| Hemoglobin < 8 g/dL (80 g/L) | Treatment should be interrupted. |

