6.3.3 Restarting or increasing dose after hematological decline

Dosing may be restarted or increased following recovery of the hematologic parameter(s) to acceptable levels. [Table 6-4](#) illustrates the maximum allowable dose that may be used after restarting or increasing doses following a previous interruption or dose decrease.

Table 6-4 Ruxolitinib maximum allowable dose levels after dose interruption or reduction due to hematological decline

| Current Hb (g/dL) | Maximum allowable dose |
|------------------------------------|---|
| < 8 | Continue hold |
| 8 to < 10 | 5 mg bid for at least 2 weeks, if stable may increase to 10 mg bid |
| 10 to < 12 | 10 mg bid for at least 2 weeks, if stable may increase to 15 mg bid |
| ≥ 12 | 15 mg bid for at least 2 weeks, if stable may increase to 20 mg bid |
| Current PLT (x 10 ⁹ /L) | Maximum allowable dose |
| < 50 | Continue hold |
| 50 to < 75 | 5 mg bid for at least 2 weeks, if stable may increase to 10 mg bid |
| 75 to < 100 | 10 mg bid for at least 2 weeks, if stable may increase to 15 mg bid |
| ≥ 100 | 15 mg bid for at least 2 weeks, if stable may increase to 20 mg bid |
| Current ANC (x 10 ⁹ /L) | Maximum allowable dose |
| < 1.0 | Continue hold |
| 1.0 to < 1.5 | 5 mg bid for at least 2 weeks, if stable may increase to 10 mg bid |
| 1.5 to < 2.0 | 10 mg bid for at least 2 weeks, if stable may increase to 15 mg bid |
| ≥ 2.0 | 15 mg bid for at least 2 weeks, if stable may increase to 20 mg bid |

Dose increases should be in increments of 5 mg bid and should not occur more often than every 2 weeks.

When restarting ruxolitinib after dose interruption, the Hb, PLT, and ANC levels must be considered to determine the restart dose, regardless of which level caused the dose interruption. The lowest calculated dose per [Table 6-4](#) should be used. The restart dose should be at least 5 mg LESS than the dose that resulted in the interruption.

Patients who required dose interruption while receiving a dose of 5 mg bid may resume at a dose of 5 mg bid or 5 mg qd, but never higher, once:

- Hb is ≥ 10 g/dL
- PLT is $\geq 75 \times 10^9$ /L,
- and ANC is $\geq 1.5 \times 10^9$ /L

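### Sections 6.3.2 and 6.3.3 give inconsistent restart instructions after a hematologic hold, and it is unclear whether Table 6-4 sets the restart dose or only a ceiling

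*Protocol*

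**What the plan says.** Protocol Section 6.3.2 covers holds for low platelets, neutrophils or hemoglobin. Once counts recover, "dosing may be restarted at 5 mg twice daily and gradually increased based on careful monitoring of blood cell counts". The sentence does not distinguish by count level or by dose before the hold, and it does not refer to Section 6.3.3.

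Section 6.3.3 covers the same event in more detail:

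- Table 6-4 "illustrates the maximum allowable dose that may be used after restarting or increasing doses following a previous interruption or dose decrease". Its title and column headings also call the values maximum allowable doses.
- At restart, "the Hb, PLT, and ANC levels must be considered to determine the restart dose, regardless of which level caused the dose interruption".
- Of the three table values, "The lowest calculated dose per [Table 6-4](#) should be used".
- In addition, "The restart dose should be at least 5 mg LESS than the dose that resulted in the interruption".
- The top row for each count reads "15 mg bid for at least 2 weeks, if stable may increase to 20 mg bid".
- Patients held while on 5 mg bid "may resume at a dose of 5 mg bid or 5 mg qd, but never higher, once" three count thresholds are met (Hb at least 10 g/dL, platelets at least 75 and ANC at least 1.5, both x 10⁹/L).

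Nothing in the protocol or SAP says which section governs. SAP Section 2.4.3 makes an incorrect dose a reportable category of protocol deviation.

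**The concern.** Two adjacent sections answer one question, the dose on which a recovered patient restarts, in different ways. Section 6.3.2 names one dose for everybody. Section 6.3.3 names a calculation that can give a higher dose.

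Safety is the primary objective, and Table 3-1 includes hematology changes among its endpoints. Tolerability (Protocol Section 10.5.3.6) is measured through dose reductions and interruptions. Relative dose intensity (SAP Section 2.4.6.1) divides by a planned dose, and the planned dose after a restart is unclear if the restart rule is unclear. All centers are pooled in a single arm, so any difference in how sites read the two sections goes straight into these summaries. Protocol Section 12 allows no authorized deviations, so the reference dose for judging a deviation needs to be known.

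**Working it through.** The plan has no figure of its own to reproduce, so the check applies each rule to the same patient.

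**Inputs.** From Section 6.3.2: restart at 5 mg bid. From Table 6-4, by recovered band:

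| Band | Hb (g/dL) | PLT (x 10⁹/L) | ANC (x 10⁹/L) | Table value |
|---|---|---|---|---|
| Low | 8 to <10 | 50 to <75 | 1.0 to <1.5 | 5 mg bid |
| Middle | 10 to <12 | 75 to <100 | 1.5 to <2.0 | 10 mg bid |
| Top | ≥12 | ≥100 | ≥2.0 | 15 mg bid |

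Pre-hold doses run from 5 to 25 mg bid. Table 6-2 allows 20 mg bid from Week 9 and 25 mg bid from Week 13, so the higher doses can occur.

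**Rule under Section 6.3.3, if the table gives the dose.** Restart dose = min(lowest of the three table values, pre-hold dose − 5 mg bid). The subtraction is read per dose, because the section's own increments are 5 mg bid.

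| Dose at hold (mg bid) | 6.3.2 (mg bid) | 6.3.3, all counts top (mg bid) | Ratio | 6.3.3, lowest count middle (mg bid) | Ratio |
|---|---|---|---|---|---|
| 25 | 5 | min(15, 20) = 15 | 3 | min(10, 20) = 10 | 2 |
| 20 | 5 | min(15, 15) = 15 | 3 | min(10, 15) = 10 | 2 |
| 15 | 5 | min(15, 10) = 10 | 2 | min(10, 10) = 10 | 2 |
| 10 | 5 | min(15, 5) = 5 | 1 | min(10, 5) = 5 | 1 |

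If any count is in the low band, Section 6.3.3 gives 5 mg bid for every pre-hold dose of 10 mg bid or more, and the sections agree.

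**How special the threefold case is.** Three counts in three bands make 27 combinations. At least one count is low in 27 − 8 = 19. None is low but at least one is middle in 8 − 1 = 7. All are top in 1. For a hold at 20 or 25 mg bid, Section 6.3.3 therefore gives 5 mg bid in 19 combinations, 10 in 7 and 15 in 1. These are counts of table cells, not of patients. The documents do not say how many patients fall in each.

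**Per dose or per day.** If the 5 mg were taken off the daily total, a hold at 10 mg bid (20 mg/day) would allow up to 20 − 5 = 15 mg/day, against 10 mg/day under Section 6.3.2. A hold at 15 mg bid (30 mg/day) would allow up to 25 mg/day. The results for 20 and 25 mg bid would not change, because the table's 30 mg/day (15 mg bid) is then the limit: 40 − 5 = 35 and 50 − 5 = 45 both exceed it. The per-dose reading is the more natural one, but the text does not state it.

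**Hold at 5 mg bid.** This is the starting dose for entry platelets of 50 to <100 (Section 6.3.4). Both sections allow resumption at 5 mg bid. Section 6.3.2 then allows gradual increase. Section 6.3.3 rules out anything higher without saying whether that applies only on resumption or also later.

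**The case against.** The strongest reply is that the sections fit together as start low, cap high. Section 6.3.2 is permissive. Table 6-4 is labeled as a set of maxima, and 5 mg bid is at or below every non-hold row. The instruction to take the lowest value can be read as saying which of three maxima binds. The reduction from the pre-hold dose is also an upper limit, and its wording allows a larger cut.

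Much of this stands. A reader might infer that the sections cannot be reconciled at all; the documents do not support that, because the ceiling reading is available. The reply does not settle the matter, though. Section 6.3.3 uses the counts to determine the restart dose and says the lowest table value should be used, which is more than a ceiling needs. If every restart were at 5 mg bid, choosing the lowest of three values would do nothing at restart, and the reduction rule would be met automatically after any hold at 10 mg bid or more. Under the ceiling reading itself, two sites could restart the same fully recovered patient at 5 and at 15 mg bid, and both would comply.

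Four other inferences go too far:

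- That Section 6.3.3 bars any later increase after a hold at 5 mg bid. The limit is attached to resumption and may apply only there.
- That a patient restarted at 5 mg bid needs 4 weeks to reach 15 mg bid. Two steps at 2 weeks each make 4 weeks, but the interval is a minimum borrowed from Section 6.3.3. Section 6.3.2 gives no interval.
- That a monitor could not classify any dosing deviation. Under the ceiling reading, a dose above the cap is clearly a deviation. SAP Section 2.4.3 also leaves the full specification to a separate planning document that is not available here.
- That Amendment 1 caused the mismatch. Its summary lists Section 6.3.2 and Table 6-3 as updated and does not list Section 6.3.3 or Table 6-4. This fits such an origin but does not show it.

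**Conclusion.** The concern holds as an internal inconsistency in the restart instructions. It is not an outright contradiction for every patient.

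A reader might take the threefold gap as the general case. It needs a hold at 20 or 25 mg bid, all three counts in the top band, and the reading that Table 6-4 gives the dose. The difference is at most twofold after a hold at 15 mg bid or with recovery only to the middle bands, and there is none after a hold at 10 mg bid. The 15 and 10 mg bid results assume that the 5 mg reduction is per dose. After a hold at 5 mg bid, the open question is later escalation; both sections permit resumption at 5 mg bid.

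The effect on recurrent cytopenia, repeat holds or dose intensity cannot be sized from the documents, and no hypothesis test is at stake. The point still merits correction, because safety is the primary objective and sites following the protocol can restart the same patient on different doses.

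**What to change.** Reconcile Section 6.3.2 with Section 6.3.3 and Table 6-4 so that one restart rule governs, with a cross-reference between them. The revised text should state:

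- whether Table 6-4 gives the restart dose or only a ceiling;
- whether the limit after a hold at 5 mg bid applies only on resumption or also to later increases;
- whether the 5 mg reduction is per dose or per day.

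The clinical team decides which rule stands; this review takes no view. The reconciled rule should then be the reference for the incorrect-dose deviation in SAP Section 2.4.3 and for the planned dose in SAP Section 2.4.6.1.

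The cost is a short clarification of one sentence in Section 6.3.2 and two in Section 6.3.3, plus a memo to sites, with no new data or visits. SAP Amendment 1 is dated 13 March 2018, after the protocol's 31 December 2017 limit on treatment. If dosing has ended, what remains is to document which rule is the reference for deviations and planned dose.
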